In the event that disruptions due to Covid-19 affect the Step 1 timeline, the first 6 participants in Step 1 will temporarily discontinue bNAbs and remain in Step 1, receiving at a minimum oral ART and safety monitoring every 12 weeks. These first 6 participants in Step 1 will resume dual bNAb infusions when the protocol team deems it is safe and feasible to do so. BNAb infusions are planned to occur throughout Step 1, but may resume later in the extended Step 1 schedule in the event of missed or discontinued infusions. If a child has missed more than 2 dual bNAb infusions, then dosing will be given as at the start of Step 1 upon resuming bNAbs: a VRC01LS loading dose of 30mg/kg and a 10-1074 dose of 30mg/kg will be given at the first resumed infusion visit. Maintenance dosing will follow as per protocol with VRC01LS given at 15mg/kg and 10-1074 given at 30mg/kg at each 4-weekly visit. BNAb will be resumed at the next scheduled bNAb administration visit on the extended Step 1 schedule (i.e., at Week 12, 16, 20, 24, 28, 32, 36, etc.) and participants may enter Step 2 (if open) on

the day of the 3rd resumed bNAb infusion visit or later (8 weeks or later after resuming monthly bNAb infusions).

SMC Review of Safety and PK Data from Step 1 (first 6 participants)

Safety, PK, and viral suppression data for the first 6 participants from Step 1 will be reviewed within 8-10 weeks (**or as soon as is feasible in the event of Covid-19 related delays**) by the study team, sponsor, and SMC. (*No changes to the remainder of this subsection.*)

Step 2 (all participants)

Following a successful Step 1 review, Step 2 may begin. Step 2 will begin after a participant has spent at least 8 weeks in Step 1 (**and has completed at least 2 consecutive dual bNAb infusion visits with the third or later dual bNAb infusion scheduled for the Step 2 entry visit**). (*No changes to the remainder of this paragraph.*)

3. Section 4. Study Design: The following subsections have been revised to read:

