All Step 1-3 participants must be from the EIT Study. After approval, Step 1 will begin for a maximum of 6 participants, all of whom will have participated in the PK Step (3 from each PK Step group), and all of whom will have been >12 weeks from last bNAb dosing. ART is continued throughout Step 1, and all participants receive both 10-1074 and VRC01LS. Following a recommendation from the study team and the SMC to increase the maintenance dosing based on the PK Step, a VRC01LS loading dose of 30 mg/kg will be given at the start of Step 1, followed by 15mg/kg dosing at each 4-weekly visit, and 10-1074 dosing will be at 30mg/kg at each 4-weekly visit. At Week 0, Week 4, and Week 8 doses of Step 1, PK testing for both bNAbs will occur prior to infusion, and at Weeks 0 and 4 only at end of infusion, 1 hour post-infusion, 1 day post-infusion, and 1 week post-infusion. HIV-1 RNA will be checked every 4 weeks in Step 1. The first 6 participants in Step 1 will continue in this Step, receiving both oral ART and dual bNAb infusions, until the second study team/SMC review occurs. This review of safety and PK data will occur within 8-10 weeks (**or as soon as is feasible in the event of Covid-19 related delays**) of the 6th participant's Week 8 PK sampling.

In the event that disruptions due to Covid-19 affect the Step 1 timeline, the first 6 participants in Step 1 will temporarily discontinue bNAbs and remain in Step 1, receiving at a minimum oral ART and safety monitoring every 12 weeks. These first 6 participants in Step 1 will resume dual bNAb infusions when the protocol team deems it is safe and feasible to do so. BNAbs are planned to occur throughout Step 1, but may resume later in the extended Step 1 schedule in the event of missed or discontinued infusions. If a child has missed more than 2 dual bNAb infusions, then dosing will be given as at the start of Step 1 upon resuming bNAbs: a VRC01LS loading dose of 30mg/kg and a 10-1074 dose of 30mg/kg will be given at the first resumed infusion visit. Maintenance dosing will follow as per protocol with VRC01LS given at 15mg/kg and 10-1074 given at 30mg/kg at each 4-weekly visit. BNAbs will be resumed at the next scheduled bNAb administration visit on the extended Step 1 schedule (i.e., at Week 12, 16, 20, 24, 28, 32, 36, etc.) and participants may enter Step 2 (if open) on the day of the 3rd resumed bNAb infusion visit or later (8 weeks or later after resuming monthly bNAb infusions).

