Additional enrollments **to Step 1** will not occur until approval is granted. If the PK data are in range and no dosing changes for the bNabs are required, the dosing used in Step 1 will continue to be used for the remainder of the study unless new data emerges requiring additional review.

After approval is granted from this second review, the first 6 Step 1 participants will enter Step 2 and discontinue ART, provided they have been in Step 1 for at least 8 weeks; **have completed at least 2 consecutive dual bNAb infusion visits with the third or later dual bNAb infusion scheduled for the Step 2 entry visit;** and have remained with viral suppression <40 copies/mL (Table 5). Additional participants will also enroll in Step 1 at this time (both those who previously participated in the PK Step, and new participants). These participants may also proceed to Step 2 and discontinue ART after 8 weeks in Step 1, if they remain with viral suppression <40 copies/mL. A participant who experiences a confirmed viral rebound \geq 40 copies/mL in Step 1 will discontinue bNabs, complete visit procedures equivalent to those outlined for Step 1 Week 8, and enter Step 3. *(No changes to the remainder of this subsection.)*

6. Section 6.3.1. VRC01LS Dose Calculation Instructions. The first paragraph has been revised to read:

VRC01LS will be dosed at 30mg/kg at the first infusion visit, followed by 10mg/kg maintenance at subsequent infusion visits in the PK Step. Following a recommendation to increase the maintenance dosing of VRC01LS based on review of data from the PK Step, VRC01LS will be dosed at 30mg/kg at the first Step 1 infusion visit, followed by 15mg/kg maintenance at subsequent Step 1 infusion visits. **If a child misses more than 2 doses in Step 1, then VRC01LS will be reinitiated as a loading dose of 30mg/kg IV at the first resumed infusion visit followed by 15mg/kg IV every 4 weeks.**

7. Section 6.4.1. Preparation of VRC01LS IV Solution. This section has been revised to read:

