After approval is granted to begin Step 1, 6 of the first 12 PK Step participants will begin dual bNAb treatment per the dosing and follow-up schedule in Table 24. The first 6 Step 1 participants will include 3 participants from each group in the PK Step; these participants may be the first 6 PK Step participants, but this is not required. **In Step 1 dosing for VRC01LS is 30mg/kg load followed by 15mg/kg maintenance, and for 10-1074 30mg/kg.** These Step 1 participants will receive enhanced PK testing for both bNAbs at the Week 0 and Week 4 visits, with pre-infusion testing, testing at end of infusion, 1 hour post-infusion, 1 day post-infusion and 1 week post-infusion (all other PK testing for these participants will be trough pre-dose testing). A review of the safety and PK data for the first 2 dual bNAb doses will occur for these 6 participants. While awaiting this review (see Section 13.8), all 6 participants will remain in Step 1 per follow-up outlined in Table 24, with 4-weekly dual bNAb treatment and ongoing oral ART. Additional enrollments will not occur until approval is granted. **If the PK data are in range and no dosing changes for the bNAbs are required, the dosing used in Step 1 will continue to be used for the remainder of the study unless new data emerges requiring additional review.**

12. Section 6.3.1. VRC01LS Dose Calculation Instructions. The first paragraph has been revised to read: VRC01LS will be dosed at 30mg/kg at the first infusion visit, followed by 10mg/kg maintenance at subsequent infusion visits in the PK Step. Following a recommendation to increase the maintenance dosing of VRC01LS based on review of data from the PK Step, VRC01LS will be dosed at 30mg/kg at the first Step 1 infusion visit, followed by 15mg/kg maintenance at subsequent Step 1 infusion visits.

13. Section 6.4.2. Preparation of 10-1074 IV Solution. This section has been revised to read:

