Although chronically-infected adults receiving either VRC01 or 10-1074 did not achieve long-term viral suppression off ART, there are important differences between these prior studies and the proposed combination study in early-treated children, including: 1) previous trials did not use a combined approach to prevent the development of resistance to each bNAb, which is widely regarded to be critical for suppressive treatment with bNAbs (as has been established with ART) [24, 25], and which is supported by some non-human primate data [26]; 2) viral reservoir burden is higher in chronically infected adults than in very early treated children; 3) chronically infected adults have pre-existing resistance to VRC01 and 10-1074 (from prior immune responses to the virus) which allow for escape [20, 21], and this viral resistance would not be expected in early-treated children; 4) the prior studies employed only minimal overlap of bNAbs and ART, and a longer overlap period may reduce viral reservoir sufficiently to allow for a longer period off ART, and 5) immune effects of bNAbs in children with a developing immune system may be different than in adults, and may facilitate induction of more potent autologous cellular and humoral immune responses against HIV-1. Other monoclonal antibodies targeting HIV co-receptors have demonstrated the ability to maintain viral suppression in a majority of adult participants for over a year [27] or during the period of antibody administration [28].

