6.3. Schedule of Intervention and Dosing

The first 12 eligible and consenting participants will receive 3 doses of a single bNAb (participants 1, 3, 5, 7, 9, 11 receive VRC01LS, and 2, 4, 6, 8, 10, 12 receive 10-1074); dosing for VRC01LS is 30mg/kg load followed by 10mg/kg maintenance, and for 10-1074 30mg/kg. Oral ART will continue during the PK Step. For the PK Step, PK measurements will occur at end of infusion, 1 hour post-infusion, 1 day post-infusion, 1 week post-infusion, 2 weeks post-infusion, and 4 weeks post-infusion (Table 1). Pre-infusion PK testing will also occur at Weeks 4 and 8. After the PK Step, monitoring will occur as outlined in 13.8.

After approval is granted to begin Step 1, 6 of the first 12 PK Step participants will begin dual bNAb treatment per the dosing and follow-up schedule in Table 2. The first 6 Step 1 participants will include

3 participants from each group in the PK Step; these participants may be the first 6 PK Step participants, but this is not required. These Step 1 participants will receive enhanced PK testing for both bNAbs at the Week 0 and Week 4 visits, with pre-infusion testing, testing at end of infusion, 1 hour post-infusion, 1 day post-infusion and 1 week post-infusion (all other PK testing for these participants will be trough pre-dose testing). A review of the safety and PK data for the first 2 dual bNAb doses will occur for these 6 participants. While awaiting this review (see Section 13.8), all 6 participants will remain in Step 1 per follow-up outlined in Table 2, with 4-weekly dual bNAb treatment and ongoing oral ART. Additional enrollments will not occur until approval is granted.

After approval is granted from this second review, the first 6 Step 1 participants will enter Step 2 and discontinue ART, provided they have been in Step 1 for at least 8 weeks and have remained with viral suppression <40 copies/mL (Table 3). Additional participants will also enroll in Step 1 at this time (both those who previously participated in the PK Step, and new participants). These participants may also proceed to Step 2 and discontinue ART after 8 weeks in Step 1, if they remain with viral suppression <40 copies/mL. A participant who experiences a confirmed viral rebound ≥ 40 copies/mL in Step 1 will discontinue bNAbs, complete visit procedures equivalent to those outlined for Step 1 Week 8, and enter Step 3.

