#### 4.3. Exploratory objectives

1. Compare trough VRC01LS and 10-1074 levels at Step 2 entry between children who ultimately remained suppressed (<400 through Step 2) versus those who rebound to  $\geq 400$  during Step 2 (restricting to children who start Step 2). Sub-analysis of levels for children who were in Step 1a (first six children) will be performed (as these six children received bNAbs in addition to ART for 32 weeks whereas subsequent children received bNAbs in addition to ART for 8 weeks).
2. Compare trough levels at end of Step 2 for children suppressed (<400 through Step 2) to levels at time of rebound to  $\geq 400$  for children who rebound during Step 2 (restricting to children who start Step 2).
3. Correlate trough levels at Step 2 entry with time of rebound  $\geq 400$  with censoring at 32 weeks (restricting to children who start Step 2).
4. Correlate trough levels at end of Step 2 for children suppressed (<400 through Step 2) and trough levels at time of rebound to  $\geq 400$  for children who rebound during Step 2 with time to rebound (censoring at 32 weeks).
5. Evaluation of potential risk factors for viral rebound to  $\geq 400$  copies/mL at/before 24 weeks in Step 2 (yes/no) (restricting to children who start Step 2). Risk factors may include demographic variables, HLA type, baseline plasma HIV RNA and PBMC DNA prior to ART (from the EIT study), PMBC DNA at Step 1 and Step 2 entry, history of prior virologic rebound on ART, duration of dual bNAb treatment (extended >8 weeks for participants in

Step 1a versus 8 weeks for other participants), trough PK values for each bNAb during Step 2 (time dependent variable), and presence of pre-defined HIV envelope sequences associated with resistance to either bNAb (earliest available in life, closest available prior to rebound, and at rebound). The extent of risk factors considered will be dependent on availability of results for these factors at the time of analysis. Analyses will compare characteristics of participants who experience rebound versus those who do not experience rebound using Fisher's Exact Test for categorical variables and Wilcoxon's Test for continuous variables).

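### The rebound analysis defines duration of dual-antibody treatment by Step 1a membership, which also marks prior PK Step exposure, so the contrast cannot isolate duration

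*SAP*

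**What the plan says.** SAP 4.3 item 5 evaluates potential risk factors for rebound to 400 copies/mL or more by Week 24 of Step 2, among children who start Step 2. One candidate is "duration of dual bNAb treatment (extended >8 weeks for participants in" Step 1a, versus 8 weeks for other participants. Rebounders and non-rebounders are compared with Fisher's exact test or Wilcoxon's test. No stratification or adjustment is described. Item 1 of the same section sets Step 1a apart for a sub-analysis of trough levels and gives 32 versus 8 weeks of overlap as the only reason.

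On who is in Step 1a, Letter of Amendment #2 (item 11, Section 6.3) says: "The first 6 Step 1 participants will include 3 participants from each group in the PK Step". Protocol Section 6.3 says the PK Step children "will receive 3 doses of a single bNAb", and Section 4 describes the first six Step 1 children as "all of whom will have been >12 weeks from last bNAb dosing".

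On who is in Step 1b, Letter of Amendment #3 (item 5, Section 6.3) says: "Additional participants will also enroll in Step 1 at this time (both those who previously participated in the PK Step, and new participants".

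PK Step participation does not appear in the factor list of item 5, among the baseline characteristics in SAP 4.2.1, or in the report contents in SAP 5.

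**The concern.** The factor is named as a duration but built from a cohort label, and that label carries a second exposure. Every Step 1a child had earlier single-antibody infusions; most or all Step 1b children had none. One-factor tests cannot tell the two apart, and nothing else in the plan does.

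The question is of real interest to the investigators. Section 2.1.2 argues that "a longer overlap period may reduce viral reservoir sufficiently to allow for a longer period off ART", so a lower rebound rate in Step 1a would naturally be read as support for that idea. Nor is prior exposure treated as trivial. Section 5.4.2 excludes previous receipt of either antibody, with an exception only for the PK Step, and every Step 1a child entered under that exception.

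The direction of any bias is unknown. Earlier exposure might help. Exposure to one antibody at a time might instead favour resistance, since Section 2.1.2 regards combined use as critical to preventing it, although the PK Step infusions were given on ART. The contrast could therefore overstate a benefit of longer overlap or hide one.

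**Working it through.** The documents give no sample size, power or expected effect for this comparison, so there is no figure to reproduce. The check is a count of who carries which exposure, followed by the consequence for the contrast.

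**Inputs**
- PK Step children: 12 (Section 4), ignoring replacements. Up to 4 may be non-EIT children, who cannot enter Step 1.
- Step 1a: 6 children, all from the PK Step.
- EIT children expected: 20 to 36 (Section 5.5). Assume all enter Step 1 and Step 2, so Step 1b has 20 − 6 = 14 to 36 − 6 = 30 children.

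**PK Step children potentially available to Step 1b**
- No non-EIT children in the PK Step: 12 − 6 = 6.
- Four non-EIT children in the PK Step: 12 − 4 − 6 = 2.
- So 2 to 6 are available. The number who actually enter may be as low as 0.

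**Overlap as described in the SAP (4-weekly dual infusions before Step 2 Day 0)**
- Step 1a: 32 / 4 = 8 infusions. Step 1b: 8 / 4 = 2 infusions.

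**Layout of the two exposures**

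| Group | PK Step yes | PK Step no |
|---|---|---|
| Step 1a | 6 (100%) | 0 |
| Step 1b, 14 children | 0 to 6 (0 to 43%) | 14 to 8 |
| Step 1b, 30 children | 0 to 6 (0 to 20%) | 30 to 24 |

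The two factors are completely aliased if no other PK Step child enters Step 1b, and strongly associated otherwise.

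**How much of a PK Step effect would appear as duration**

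Suppose duration has no effect, and PK Step exposure changes the rebound risk by d, whichever antibody was given. With k PK Step children among m in Step 1b:
- Step 1a risk = r + d
- Step 1b risk = r + d × k/m
- Apparent duration effect = d × (1 − k/m)

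| m | k = 0 | k = 2 | k = 6 |
|---|---|---|---|
| 14 | 100% of d | 1 − 2/14 = 86% | 1 − 6/14 = 57% |
| 30 | 100% of d | 1 − 2/30 = 93% | 1 − 6/30 = 80% |

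These are shares of an unknown d. The documents give no basis for its size or sign.

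**What a split could show**

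Duration can be compared at fixed PK Step exposure only within the PK Step = yes column, at most 6 v 6. Two-sided Fisher p-values there are:
- 6/6 v 1/6: 2 × 7/924 = 0.015
- 6/6 v 2/6: 2 × 28/924 = 0.061

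Only a near-total separation would reach 0.05. The unsplit contrast is weak too: for true proportions of 70% v 30%, exact power is 34% for 6 v 14, 32% for 6 v 22 and 35% for 6 v 30.

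**The case against.** The case for leaving the plan alone is substantial. SAP 4.1.4 calls these analyses descriptive and exploratory. Item 5 says only what the factors may include, so PK Step participation could be added without a change. No primary or secondary outcome in SAP 4.2 depends on the factor. The PK Step infusions were given on ART and followed by a gap of more than 12 weeks. Letter of Amendment #2 (item 10) has the first six chosen without regard to their individual PK results. Coding details belong to the Analysis Implementation Plan, which is not among the documents. All of this stands and lowers the priority, but none of it turns the cohort label into a measure of duration.

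Three stronger readings are tempting and are not supported.

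- A reader might infer that the SAP will report a Step 1a difference as a benefit of longer overlap. It does not say so. The risk lies in how the named factor would be read.
- A reader might infer that Step 1a children also had more ART before withdrawal. The longer Step 1 is the exposure under study, not a separate confounder. Children outside the PK Step stayed on ART over the same calendar period, and Step 1b opens only after the Step 1a review. Later entrants may have had as much ART or more.
- A reader might infer that Covid pauses make the grouping wrong. Letter of Amendment #3 (item 2) says infusions "may resume later in the extended Step 1 schedule in the event of missed or discontinued infusions", but this is a contingency. The SAP describes in the past tense 4-weekly infusions up to Week 32, and nothing shows that a pause occurred. Even after a pause, Step 2 entry is no earlier than the third resumed infusion. One infusion before the pause and two after it would cover 3 × 4 = 12 weeks in total, still above 8. A pause would undermine the 32-week figure in item 1 more than the grouping in item 5.

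**Conclusion.** The point holds in a limited form. As defined, the duration factor is Step 1a membership, which is tied to PK Step exposure: 100% in Step 1a, against 0 to 43% in Step 1b at 20 children and 0 to 20% at 36. A Step 1a versus other difference in rebound, in either direction, cannot be attributed to overlap duration alone. If duration had no effect, 57% to 100% of any PK Step effect would pass into the contrast.

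This rests on 20 to 36 children all entering Step 2, 12 PK Step children without replacement, and the same effect for either antibody. Whether PK Step exposure affects rebound at all is unknown. The matter concerns an optional exploratory factor and the primary results are unaffected, so it is a cheap improvement to consider.

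**What to change.** In SAP 4.3 item 5:

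1. Add PK Step participation (yes/no) to the listed factors.
2. Show rebound separately for Step 1a, Step 1b with PK Step and Step 1b without PK Step.
3. State that the Step 1a versus other contrast does not isolate duration of overlap.
4. Optionally, confirm the duration grouping from the number of dual infusions recorded for each child before Step 2 Day 0, since Letter of Amendment #3 permitted pauses.

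The cost is a few words in the SAP and extra table rows. PK Step membership is known, and missed infusions are recorded under Letter of Amendment #3, so no new data are needed. The downside is very small groups: the comparison within PK Step children is 6 v 0 to 6, so it should be presented as description and not as a test of duration.

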2.3. Study Hypotheses

2.3.1. Specific Aim 1: VRC01LS and 10-1074 will not be associated with serious adverse events, and median trough concentrations at the doses used will be above established target values of 200 mcg/mL and 7.5 mcg/mL respectively. At least 70% of early-treated low-reservoir children will remain with HIV-1 RNA <400 copies/mL after 24 weeks of receiving VRC01LS and 10-1074 maintenance.

2.3.2. Specific Aim 2: Measurable decline in viral reservoir as measured in blood samples will occur in some children with the addition of dual bNAb therapy to ART. Viral reservoir size prior to receiving ART and prior to receiving VRC01LS and 10-1074, as determined by cell associated HIV-1 DNA and other assays, is inversely correlated to viral rebound kinetics (if rebound occurs on bNAb maintenance). If present, viral rebound will not exceed 1,000 copies/mL prior to re-initiation of ART (and acute retroviral syndrome will not occur). Delayed HIV-1 RNA and DNA suppression patterns in early life will correlate with viral rebound during the ATI. Baseline HIV from most children will be sensitive to VRC01LS and 10-1074, and a decrease in sensitivity will be detectable among children who experience viral rebound.

2.3.3. Specific Aim 3: The breadth of humoral immune responses to HIV-infection will increase following VRC01LS and 10-1074 use. Markers of cellular immune activation may increase on bNAb maintenance. Cell-mediated immune responses to HIV-1 will be preferentially detectable among children with viral rebound.

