Although this proof-of-concept Phase I/II study will not have a control group, an observed proportion of at least 30% suppression on dual bNAb therapy would provide reasonable evidence of a positive effect of VRC01LS + 10-1074 in maintaining virologic suppression, as maintenance of HIV-1 RNA <400 copies/mL is unlikely in the absence ART, even for early-treated children. As noted above, data from children treated in the first year of life in CHER [52] and in Kenya [58] showed that few children remain suppressed to a threshold of <400 copies/mL at 6 months off ART. In CHER, only 2 of 183 children were suppressed to <400 copies/mL at 6 months (one of whom has remained suppressed for > 9 years, and the other rebounded at ~ 8 months). Additional data from Aims 2 and 3 that correlate viral reservoir (pre-ART, and pre- and post-bNabs) and maintenance of viral suppression, and

associations between immune responses and viral control, will bolster interpretation of the specific effect of VRC01LS + 10-1074 on maintenance of viral suppression.

10.1.3. Dynamics of viral decay and rebound: Based on frequent HIV RNA monitoring after ART withdrawal, the kinetics of viral rebound (if rebound occurs) will be summarized descriptively. Analyses will assess viral suppression off-ART (yes vs. no) and time to HIV RNA ≥ 400 (and ≥ 40) copies/mL, and will evaluate associations of these metrics with pre-ART and on-ART virologic and immunologic measures including immune activation and anti-HIV immune responses (binary regression; rank correlations analyzing infants with sustained undetectable HIV RNA off-ART as the lowest rank).

10.1.4. Growth assessments: Child weight and height will be measured at least every month, and WHO standardized Z-scores will be evaluated for changes over time (beginning with pre-intervention data from the EIT study), and compared with data from prior studies for children on continuous ART. Although neurodevelopmental assessments would be of interest, the small number of children in this cohort and lack of an appropriate comparator group would preclude meaningful information from being obtained from standard neurodevelopmental testing.

10.2. Data Analysis and Statistical Considerations for Specific Aim 2

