#### **4.2.2. Primary outcomes**

1. AEs will be summarized generally (any graded event) and specifically (any SAE, defined above, or any AE determined by the study team to be related to one or both bNAb

infusion). Summaries will include listings by child of all graded events and summaries by frequency of AEs by event (including all graded events and focusing on SAEs and bNAb-related AEs).

2. Cumulative proportion of children experiencing SAEs during follow-up (until 30 days after last study visit for each participant) and proportion of potentially bNAb-related events. In particular, proportions of children experiencing the following events will be summarized along with 95% exact confidence intervals (based on the Clopper-Pearson method). The denominators for the following are all participants who received at least one infusion of a bNAb in Step 1.
  - a. At least one graded AE (of any grade)
  - b. At least one grade 3 or higher AE
  - c. At least one SAE (as defined above)
  - d. At least one potentially bNAb-related AE of any grade
  - e. At least one potentially bNAb-related AE grade 3 or higher
  - f. At least one potentially bNAb-related SAE
3. Proportion of children, among those receiving at least one infusion of a bNAb in Step 1, who maintain HIV-1 RNA in plasma less than 400 copies/mL at least 32 weeks after initiating dual bNAb treatment (i.e., 24 weeks after withdrawal of standard ART, which is through week 24 of Step 2) will be calculated along with a 95% confidence interval (based on exact Clopper-Pearson confidence limits).
4. Repeat #3 but considering only those children who enter Step 2 and discontinue ART.
5. Repeat #3 and #4 but considering the maintenance of less than 40 copies/mL (rather than 400 copies/mL).
6. Time from Step 2, Day 0 to HIV-1 RNA  $\geq$  400 copies/mL will be analyzed using Kaplan-Meier methods, with censoring at last available HIV-1 RNA measurement in Step 2 if lost to follow-up or administratively at Step 2, Week 24. This will be done among all participants receiving at least one infusion of a bNAb, and among those who entered Step 2 and discontinued ART.
7. Repeat #6 but considering time to HIV-1 RNA  $\geq$  40 copies/mL.
8. Time to re-suppression to  $<$  40 copies/mL (and  $<$  400 copies/mL) will be analyzed using Kaplan-Meier methods among those who entered Step 3 because of virologic failure in Step 2; time will be measured from the day of re-starting ART in Step 3 (Step 3 Day 0).

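### SAP 4.3 item 5 relates non-PK risk factors only to yes/no rebound, although protocol 10.1.3 also plans their association with time to rebound; add it beside the yes/no tests or say why it is left out

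*SAP*

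**What the plan says.** - **SAP 4.3 item 5** covers children who start Step 2 and sets its task as "Evaluation of potential risk factors for viral rebound to $\geq 400$ copies/mL at/before 24 weeks in Step 2 (yes/no". The candidate factors include demographics, HLA type, pre-ART plasma RNA and PBMC DNA, PBMC DNA at Step 1 and Step 2 entry, earlier rebound on ART, length of dual bNAb treatment on top of ART, troughs in Step 2 and envelope sequences. The method for categorical factors is: "Analyses will compare characteristics of participants who experience rebound versus those who do not experience rebound using Fisher's Exact Test for categorical variables". Continuous factors are handled by "Wilcoxon's Test for continuous variables".
- **Protocol 10.1.3** (Aim 1) names two outcome metrics: "Analyses will assess viral suppression off-ART (yes vs. no) and time to HIV RNA" of 400 or more (and of 40 or more) copies/mL. It "will evaluate associations of these metrics with pre-ART and on-ART virologic and immunologic measures", by binary regression and by "rank correlations analyzing infants with sustained undetectable HIV RNA off-ART as the lowest rank".
- **SAP 4.2.2 item 6** already derives the time variable: time from Step 2 Day 0 to "HIV-1 RNA $\geq$ 400 copies/mL will be analyzed using Kaplan-Meier methods", with a censoring rule. Item 7 repeats it at 40 copies/mL. Neither uses covariates.
- **SAP 4.3 items 3 and 4** correlate trough levels with time to rebound.
- **Protocol 2.3.2** (Aim 2) hypothesises that reservoir size "is inversely correlated to viral rebound kinetics (if rebound occurs on bNAb maintenance". Protocol 10.2.1 plans to correlate reservoir markers with rebound kinetics, and 10.3.5 will explore immune responses against them. SAP 2.2 says that objectives outside Aim 1 are handled separately.

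**The concern.** In item 5 a child who rebounds at Week 2 counts the same as one who rebounds at Week 24, although HIV RNA is measured throughout Step 2 and the SAP already derives time to rebound. The comparison is meant to indicate which children can stay off ART, and with 20 to 36 children there is little information to spare. The fewer children stay suppressed, the more of that information lies in when the others rebound.

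The SAP gives no reason for leaving out a metric that the protocol lists under the same aim. Its version history records that the plan for this comparison was revised, but not why. Item 5 also omits the 40 copies/mL threshold, and it has no rule for a child who leaves Step 2 early without rebound. The censoring rule in 4.2.2 would supply one.

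**Working it through.** **1. Where each item 5 factor is related to time to rebound**

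| Factor | In this SAP | Elsewhere in the plan |
|---|---|---|
| Troughs | Yes, 4.3 items 3 and 4 | – |
| Pre-ART RNA/DNA, PBMC DNA at Step entry | No | Protocol 10.1.3; also 10.2.1 as reservoir markers |
| HLA type | No | Protocol 10.1.3, if read as an immunologic measure |
| Earlier rebound on ART | No | Protocol 10.1.3, as an on-ART virologic measure; not named under Aims 2 or 3 |
| Length of ART–bNAb overlap | No | Not named in 10.1.3, 10.2.1 or 10.3.5 |

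For the last two rows, item 5 is the only analysis that either document states by name.

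**2. What yes/no scoring sets aside.** After entry, Step 2 has 4 weekly visits and then (24 − 4)/2 = 10 two-weekly visits, so 14 possible rebound times. Take n = 20 (the protocol's minimum).
- At 30% success there are 6 suppressed and 14 rebounding children. A yes/no rank test uses 6 × 14 = 84 pairs. Ordering the rebounders by time adds up to 14 × 13/2 = 91, fewer with ties.
- At 70% success the split is 14 and 6. The pairs are again 84, and ordering adds at most 6 × 5/2 = 15.

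**3. The plan's own figures.** No power, alpha or effect size is given for item 5. The nearest stated figures are the exact 95% limits in protocol 10.1.2, and they reproduce: 14/20 gives 45.7% to 88.1% (stated 46% to 88%) and 6/20 gives 11.9% to 54.3% (stated 12% to 54%). They fix the sample size and success rates used below.

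**4. Power when a factor shifts the hazard (assumed model).** Hazard = λ·exp(βx), with x standard normal and β = log(HR per SD). λ is set to give 30%, 50% or 70% rebound by Week 24. Times are moved up to the next visit and censored at Week 24. Tests are two-sided at 5% (assumed), with 4,000 trials per cell, so the Monte Carlo standard error is at most √(0.25/4000) = 0.8 points. At HR 2 per SD:

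| n | Rebound | Wilcoxon yes/no | Protocol's rank correlation | Cox score |
|---|---|---|---|---|
| 28 | 30% | 39.6% | 41.8% | 45.9% |
| 28 | 50% | 58.7% | 62.4% | 67.2% |
| 28 | 70% | 64.1% | 71.7% | 78.8% |
| 36 | 30% | 52.1% | 53.4% | 58.2% |
| 36 | 50% | 70.5% | 72.8% | 77.9% |
| 36 | 70% | 78.0% | 83.2% | 89.1% |

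Over HR 1.5 to 3 and n = 20 to 36, the gain over Wilcoxon is about 3 to 20 points for the Cox score test. For the rank correlation it is about 1 to 13 (1 to 5 at 30–50% rebound, 2 to 13 at 70%). With no effect, rejection was 4.0–5.2% for Wilcoxon and 4.7–5.8% for Cox, so about 0 to 1 point of the gap is test size. Binary factors are left out of these ranges because part of any gain over Fisher's test is only Fisher's conservatism.

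**5. Power when a factor affects whether, but not when, a child rebounds.** Logistic effect on rebound, with rebound time independent of the factor. At OR 3 per SD:

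| n | Rebound | Wilcoxon yes/no | Rank correlation | Cox score |
|---|---|---|---|---|
| 20 | 30% | 42.2% | 42.7% | 45.7% |
| 28 | 50% | 65.9% | 57.9% | 65.3% |
| 36 | 70% | 71.4% | 49.2% | 64.8% |

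Over OR 2 and 3 the Cox score test runs from 6.6 points worse to 3.5 better. The rank correlation runs from 22.2 worse to 1.5 better.

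**The case against.** The analyses are labelled descriptive and exploratory, without multiplicity adjustment, and no endpoint or stopping rule depends on item 5. Its yes/no form matches the primary efficacy proportion. Protocol 13.4.1.4 says that bNAb resistance at rebound usually arises by selection of mutations already present. Such a factor could act mainly on whether a child rebounds, and then step 5 favours the yes/no test. All of this stands.

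Four stronger readings are tempting, and the documents do not support them.
- **That time to rebound is ignored for every risk factor.** Items 3 and 4 use it for troughs.
- **That the reservoir–kinetics hypothesis goes untested.** It belongs to Aim 2, protocol 10.2.1 plans the correlation, and SAP 2.2 places other aims outside this document.
- **That the yes/no form costs a known amount of power.** Effect size, alpha and proportional hazards are all assumed here. The larger gains belong to a Cox score test, which neither document names; the protocol's own rank correlation gains less.
- **That the time-based test should lead.** Step 5 shows that either form can be the weaker one.

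What the objection does not remove is that 10.1.3 is an Aim 1 section. The SAP neither carries out its time-to-rebound association for non-PK factors nor says where it will be done.

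**Conclusion.** The point holds as a mismatch between protocol and SAP within Aim 1. For non-PK factors, item 5 keeps one of the two metrics in protocol 10.1.3 and omits time to 400 (and 40) copies/mL without explanation. For reservoir and immune measures the time association is absent from this SAP but still planned under other aims. For earlier rebound on ART, item 5 is the only stated analysis. The same is true of overlap length, which 10.1.3 does not name; there the argument is consistency with items 3 and 4 rather than a departure from the protocol.

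The possible benefit is conditional, as steps 4 and 5 show: it depends on whether a factor shifts the timing of rebound, on the share of children who rebound, and on the test chosen. This is a worthwhile low-cost improvement to an exploratory analysis.

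**What to change.** In SAP 4.3 item 5, for factors fixed at or before Step 2 entry:
- Add the association with time from Step 2 Day 0 to first HIV RNA of 400 copies/mL or more, and repeat it for 40 or more. Censor as in 4.2.2 items 6 and 7, not at the 32 weeks given in 4.3 items 3 and 4.
- Use a log-rank test for categorical factors and a Cox score test for continuous ones, with permutation p-values, the hazard ratio and its 95% CI. Alternatively, use the protocol's rank correlation, knowing that it can lose the most if timing is unrelated to the factor.
- Keep Fisher's and Wilcoxon's tests on yes/no rebound alongside, with neither approach named as lead.

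Troughs during Step 2 and sequences taken near or at rebound fall outside this addition because they are not fixed at entry. Item 5 labels the troughs time dependent, which a two-group test cannot use as such.

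If the team prefers to leave item 5 as it is, one sentence should give the reason for departing from 10.1.3, or say where the time association will be reported.

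Cost: one or two sentences and a little programming, with no new data. The downside is a second set of exploratory p-values, and a further set if the 40 copies/mL threshold is included.
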